5.2.3. Apremilast Exposure Period

In addition to the above defined phases, Apremilast Exposure Period will be used for safety analyses. This period starts on the date of either:

- (1) the first dose of IP following randomization (Week 0/Visit 2) for subjects who are treated with Apremilast 30 mg BID first;
- (2) the first dose of IP from the IP dispensed at Week 16/Visit 5 for subjects who were originally treated with placebo and are treated with Apremilast 30 mg BID at Week 16.

This period stops on either:

- (1) data cut-off date;
- (2) the day of the treatment discontinuation if the subject discontinued prior to or at Week 52/Visit 9;
- (3) the last known study day if the subject is lost to follow-up prior to Week 52/Visit 9;
- (4) Week 52/Visit 9 visit date.

Study treatment duration will also be summarized for the Apremilast Exposure Period. The outputs based on the Apremilast exposure period only have one Apremilast 30 mg BID arm.

5.2.4. Follow-up Phase

Apremilast

Statistical Analysis Plan. Protocol CC-10004-PSOR-020

Amgen INC.

For all subjects who complete the study or discontinue the study early, the Four-week Observational Follow-up Phase starts at the completion or discontinuation visit and stops at the follow-up visit or the last assessment date.

Concomitant medications are summarized based on the follow-up phase including data collected after the last dose of the study treatment up to the 28 days post-treatment for subjects who entered the observational follow-up phase.

5.3. Analysis Populations

5.3.1. Intent-to-Treat Population

The Intent-to-Treat (ITT) population includes all subjects who are randomized. Subjects will be included in the treatment arm to which they are randomized.

This is the primary population for the primary endpoint and all other quality of life and efficacy analyses. Baseline summaries and treatment compliance summaries are also based on the ITT population.

5.3.2. Per-Protocol Population

The per-protocol (PP) population includes all subjects who are in the ITT population, who receive at least one dose of IP, have both baseline and at least one post-treatment DLQI evaluation, and have no major protocol deviations which may affect analyses in the Placebo-controlled Phase. The PP population is only used to supplement the primary endpoint ITT analysis.

5.3.3. Safety Population

The safety population includes all subjects who are randomized and receive at least one dose of study drug. If a subject receives study drug other than the subject's randomized treatment assignment, then the subject is assigned to the treatment arm reflecting the treatment that the subject actually received during the study. All safety endpoints, study treatment duration, and concomitant medication summaries for the placebo-controlled phases are based on the safety population.

5.3.4. Apremilast Exposure Population

The Apremilast exposure population consists of only those subjects who receive at least one dose of Apremilast treatment, i.e., all subjects in the Apremilast 30 mg BID arm from the safety population and the subset of subjects in the placebo arm from the safety set who also enter the Apremilast Extension Phase with at least one treatment of Apremilast. The Apremilast Exposure population are only used for the safety endpoints.

5.4. Definition of baseline

Core baseline (Week 0) is used for all efficacy analyses, safety analyses for the placebo-controlled period, and summary of baseline disease characteristics.

For efficacy analysis and summary of baseline disease characteristics data, baseline is defined as the last value measured prior to or at the randomization visit.

For safety summaries, baseline is defined as the last value measured on or before the day of the first dose of double-blind treatment.

Apremilast treatment baseline is used for the summaries of safety analyses for the Apremilast Exposure Period. It is defined as the last value measured on or before the day of the first Apremilast dose.

5.5. Time Points

Time points in all analyses are based on the visits/study weeks using the following visit mapping algorithm, which may or may not be the same as the visits/study weeks as recorded in the database.

Post baseline time points in all analyses will be captured based on analysis visit window (range of study days) around the target day for each analysis visit, based on the actual day of evaluation relative to a reference date. Appropriate dates will be used to calculate the study day, e.g., date of measurement or date of specimen collection will first be used, and then the date of visits/study weeks as recorded in the database will be used. If there are multiple measurements within a time point based on the study day, then the non-missing value from the closest measurement to the planned study day will be used for that visit. If the value at a scheduled visit is missing and there is no value available within the time window based on the study day, the value at the study week will be missing.

Table 2: Table for Visit Mapping for by Time Point Analysis

Analysis Visit	Target Day	Visit Window
Baseline	1	≤ 1
Placebo-controlled Phase (for all endpoints)		
Week 2	15	2 – 21
Week 4	29	22 – 70
Week 16	113	71 – End of Placebo-controlled Phase
Apremilast Extension Phase (for efficacy endpoints)		
Week 20	141	Start of Apremilast Extension Phase – 182
Week 32	225	183 – 294
Week 52	365	295 – End of Apremilast Extension Phase
Apremilast Extension Phase (for safety endpoints)		

Apremilast

Statistical Analysis Plan. Protocol CC-10004-PSOR-020

Amgen INC.

Week 20	141	Start of Apremilast Extension Phase – 182
Week 32	225	183 – 266
Week 44	309	267 – 337
Week 52	365	338 – End of Apremilast Extension Phase

Note: Target day and visit window are relative to the date of Visit 2/Week 0 (Day 1) for randomization. Definitions for baseline and start or end of the phases are specified in [Section 5.25.2](#) and [5.4](#) for both efficacy and safety analysis.

Time points in the analyses or summaries of efficacy data over time include the scheduled study weeks per protocol, the end of a study phase, and the observational follow-up visit. Appropriate dates (e.g., date of measurement or date of specimen collection) will first be used to ensure only data (including data from scheduled, unscheduled, container visits, discontinuation, and observational follow-up visits) measured or collected within the specific analysis phase (as defined in Section 5.2) being analyzed or summarized are included, and then the visits/study weeks as recorded in the database will be used to assign one value (possibly missing) to each time point at the subject level. It is possible that multiple assessment values will fall into the same visit window. The following rule may be used to select the unique value for that analysis visit:

1. Among all assessments in the same visit window for the analysis visit, select the value with the assessment date closest to the target day of the analysis visit;
2. If the relative days from 2 assessments are equally close to, but on different sides of the target day, then the latter assessment will be used for that analysis visit;
3. If multiple assessments are available on the same relative day, then the highest value of these assessments will be used for that relative day.

The time points for summaries of safety data (laboratory parameters, vital signs and weight) are based on study week/visit for the placebo-controlled phase. For the Apremilast Exposure Period, the scheduled study weeks for placebo subjects who are treated with Apremilast 30 mg BID at Week 16 will be mapped to reflect the study weeks relative to the first dose of Apremilast (see table below).

Table 3: Adjustment and Mapping of Study Weeks for Placebo Subjects who are Treated with Apremilast 30 mg BID after Week 16 in Summary of Safety Data over Time

Original Visit	Re-Mapped Visit for subjects initially randomized to placebo
Week 16	Baseline
Week 20	Week 4
Week 32	Week 16
Week 44	Week 28
Week 52	Week 36

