Descriptive statistics will be provided for vital signs, weight, waist circumference, laboratory values (continuous measurements) by treatment and visit, including the end of phase/period visits. The baseline value, value at the time point, and change from baseline (also percent change from baseline if applicable) will be summarized for subjects who have values at baseline and at the time point.

Shift tables, that is, tables summarizing the baseline categories (normal, abnormal) versus the category at the end of the respective periods or versus the worst post-baseline category, include subjects who have values at baseline and at least one post-baseline value. Similarly, in frequency summaries of shifts from baseline at scheduled study weeks per protocol, only subjects who have values at baseline and at the corresponding time point will be included.

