10.3. Vital Sign, Weight, and Waist Circumference Measurements

The endpoints for vital sign parameters, weight, and waist circumference include:

- Observed value and change from baseline over time in vital sign parameters including temperature, pulse, and blood pressure
- Shifts from baseline to post-baseline time points and to the worst post-baseline value in terms of normal/abnormal in pulse and blood pressure (normal ranges are defined as: 60-100 beats/minute for pulse, 90-140 mmHg for systolic blood pressure, and 60-90 mmHg for diastolic blood pressure)
- Observed value, change and percent change from baseline over time in weight and waist circumference

Summary statistics (N, Mean, STDEV, Median, Minimum, and Maximum) of observed values, changes from baseline, and percent change from baseline (applicable for weight and waist circumference) will be provided over time. Frequency summaries (shift tables) of shifts from baseline to post-baseline time points and to the worst post-baseline value in terms of normal/abnormal will be provided for pulse and blood pressure.

Frequency summaries of percent change in weight from baseline to the end of the study phase/period will be provided by baseline BMI category (<18.5, 18.5 to < 25, 25 to < 30, \geq 30 kg/m²) and by baseline weight category (< 70, \geq 70 to < 85, \geq 85 to < 100, and \geq 100 kg). The categories of weight change (kg) and percent change (%) are < -20, \geq -20 to < -10, \geq -10 to < -5, \geq -5 to < 0, 0, > 0 to \leq 5, > 5 to \leq 10, > 10 to \leq 20, and > 20.

A subject data listing of all vital sign parameters, weight, and waist circumference data with abnormal flags where applicable and study phase/period flags will be provided.

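### By-visit safety summaries for the Apremilast Exposure Period put two cohorts in one column, although both are measured at only 2 of 9 scheduled time points for weight and vital signs, 2 of 7 for waist circumference and 1 of 4 for laboratory values

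*SAP*

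**What the plan says.** SAP 5.5 re-labels visits for the exposure period: "the scheduled study weeks for placebo subjects who are treated with Apremilast 30 mg BID at Week 16 will be mapped" to weeks counted from the first apremilast dose. The title of Table 3 shows who is re-labelled: "Adjustment and Mapping of Study Weeks for Placebo Subjects who are Treated with Apremilast 30 mg BID after Week 16 in Summary of Safety Data". Study Weeks 16, 20, 32, 44 and 52 become Baseline and Weeks 4, 16, 28 and 36. The last two rows read "Week 44 Week 28" and "Week 52 Week 36". Subjects who received apremilast from Week 0 are not re-mapped.

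SAP 5.2.3 fixes the layout: "The outputs based on the Apremilast exposure period only have one Apremilast 30 mg BID arm". The opening text of SAP Section 10 confirms that the two cohorts are combined whether apremilast began at Week 0 or Week 16.

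The same section plans summaries at each visit: "Descriptive statistics will be provided for vital signs, weight, waist circumference, laboratory values (continuous measurements) by treatment and visit". SAP 10.3 adds, as an endpoint, "Observed value, change and percent change from baseline over time in weight and waist circumference". SAP 10.2 plans the equivalent over-time summaries for laboratory parameters. Neither document splits these exposure-period tables by original arm or says which subjects supply each week.

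**The concern.** A single column ordered by week on drug invites the reader to follow it downwards as a time course. That works only if broadly the same subjects stand behind successive rows. Here the switchers' re-mapped weeks mostly fall between the starters' visits, so many rows come from one cohort alone and neighbouring rows can come from different people.

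The cohorts are not interchangeable samples. A starter enters the exposure population with one dose of apremilast. A switcher must first have gone through the placebo phase and entered the extension (SAP 5.3.4). Differences in selection and plain sampling error would therefore appear in the table as movement over time.

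Weight is where this matters most. Clinically significant change in body weight is part of a listed secondary endpoint (Protocol Table 2), unexplained weight loss is singled out in Protocol 6.5.2, and Protocol 9.7 plans weight change by visit.

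**Working it through.** **Inputs.** The re-mapping comes from SAP 5.5 Table 3. The assessment schedule comes from the Table of Events (Protocol Table 3): weight and vital signs at Weeks 2, 4, 16, 20, 32, 44 and 52; waist circumference at the same visits except Week 44; laboratory tests at Weeks 16, 32 and 52.

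**Reproducing Table 3.** Re-mapped week = study week − 16. For 16, 20, 32, 44 and 52 this gives 0 (Baseline), 4, 16, 28 and 36, which matches the SAP exactly.

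**Overlap of scheduled post-baseline weeks.** SAP 5.5 names laboratory parameters, vital signs and weight for this mapping. The waist row assumes the same treatment.

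| Parameter | Week 0 starters | Week 16 switchers, re-mapped | Distinct weeks | Both cohorts |
|---|---|---|---|---|
| Weight, vital signs | 2, 4, 16, 20, 32, 44, 52 | 4, 16, 28, 36 | 7 + 4 − 2 = 9 | 4, 16 (2 of 9) |
| Waist circumference | 2, 4, 16, 20, 32, 52 | 4, 16, 36 | 6 + 3 − 2 = 7 | 4, 16 (2 of 7) |
| Laboratory values | 16, 32, 52 | 16, 36 | 3 + 2 − 1 = 4 | 16 (1 of 4) |

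**Order of rows for weight and vital signs.** Week 2 starters; 4 both; 16 both; 20 starters; 28 switchers; 32 starters; 36 switchers; 44 starters; 52 starters. The steps 20 to 28, 28 to 32, 32 to 36 and 36 to 44 are complete changes of cohort. Weeks 44 and 52 are both starters, so the alternation stops at Week 44. For laboratory values the order is both, starters, switchers, starters.

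**Row sizes (assumption).** Take 276 randomized 2:1 with 24% lost before Week 16 in each arm (SAP 4.4): 184 × 0.76 ≈ 140 starters and 92 × 0.76 ≈ 70 switchers. With no later dropout, n from Week 16 onwards runs 210, 140, 70, 140, 70, 140, 140.

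**What the column can do with no change in anyone (illustration).** Suppose the mean change is constant at −1.0 in starters and 0.0 in switchers, with one third switchers in the shared rows. The pooled column then reads:

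| Week | 2 | 4 | 16 | 20 | 28 | 32 | 36 | 44 | 52 |
|---|---|---|---|---|---|---|---|---|---|
| Mean change | −1.0 | −0.67 | −0.67 | −1.0 | 0.0 | −1.0 | 0.0 | −1.0 | −1.0 |

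The whole difference between cohorts appears at every swap.

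**Chance alone (illustration).** The documents give no SD of weight change; assume 3 to 5 kg. SE of the difference between two cohort means = SD × √(1/140 + 1/70) = SD × 0.146, which is 0.44 kg (SD 3) to 0.73 kg (SD 5). Multiplying by 1.96 gives ±0.86 to ±1.43 kg between adjacent single-cohort rows when the true means are equal.

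**The case against.** The case for leaving the tables alone has real content. They are descriptive, and Protocol 9.7 plans no inferential safety testing. N is among the statistics listed in SAP 10.2 and 10.3, so the swing in row size would be visible. Table 3 lets a careful reader work out who is in each row. Weight safety does not rest on this table: SAP 10.3 also gives categorised percent weight change to the end of the period, and the randomized comparison sits in the placebo-controlled tables. Table shells are not part of the documents, so a footnote cannot be ruled out.

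Most of this stands and limits the point to a minor one. It does not remove it. A changing N suggests missed visits or dropout; it does not say that the subjects were replaced.

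Some stronger readings should be resisted.

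- A reader might infer that a real trend is lost or corrupted. The documents do not support that. Every scheduled row after Week 16 holds one cohort, so starters can still be followed at Weeks 20, 32, 44 and 52, and switchers at Weeks 28 and 36. What is missing is the label.
- A reader might apply 2 of 9 to all by-visit safety tables. It holds for weight and vital signs only.
- A reader might object that the baselines come from different visits. SAP 5.4 measures each subject from the last value on or before the first apremilast dose, which is the proper reference for time on drug.
- A reader might take the kilogram range as an expected bias. It is sampling noise under an assumed SD.

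**Conclusion.** The point holds as a matter of presentation with a cheap remedy. As planned, the exposure-period by-visit column mixes cohort with time on drug. Both cohorts are present at 2 of 9 scheduled post-baseline time points for weight and vital signs, 2 of 7 for waist circumference if mapped alike, and 1 of 4 for laboratory values. For weight and vital signs, the four steps between Weeks 20 and 44 are unlabelled changes of cohort and should not be read as change within patients. Shift tables by time point share the problem because they use the same rows.

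AE tables, exposure-adjusted incidence rates, marked abnormalities, worst-value shifts and end-of-period summaries are not affected.

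The counts refer to scheduled assessments and need no assumption beyond the mapping of waist circumference; early-termination or unscheduled values could add a few observations to other rows. The row sizes assume equal attrition before Week 16 and none after it. The ±0.9 to ±1.4 kg range also depends on the assumed SD and is illustrative only.

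**What to change.** Amend SAP 5.2.3, the general text of Section 10, 10.2 and 10.3 so that by-visit exposure-period summaries appear in two columns: apremilast from Week 0 and apremilast from Week 16. The general text of Section 10 must change with the others, because its combining of cohorts regardless of start time would otherwise contradict them.

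Give a pooled value only where both cohorts have a scheduled assessment of that parameter: Weeks 4 and 16 for weight, vital signs and waist circumference, and Week 16 only for laboratory values, which have no scheduled Week 4 test. State in SAP 5.5 whether waist circumference follows Table 3. Leave the pooled tables that are not by visit as they are.

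The cost is wider descriptive tables and a smaller n per column. SAP 5.2.2 already groups extension-phase tabulations by original arm, so the layout exists. If two columns are not wanted, a label on each row naming the contributing cohort would remove most of the risk of misreading.

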6. SUBJECT DISPOSITION

The number and percentage of screened subjects randomized (as recorded in the IVRS database) and not randomized will be summarized. The failed inclusion/exclusion criteria of subjects who were screened and not randomized will be included in the summary. The percentages will be based on the number of subjects screened. For patients who were rescreened, the last screening status will be considered for the summary.

Randomized subjects included in the ITT population, PP population, safety population, and Apremilast Exposure population will be summarized by treatment arm.

The numbers and percentages of randomized subjects who entered, completed, and discontinued from the following protocol phases will also be summarized by treatment arm. All the percentages will be based on the number of subjects randomized.

- Placebo-controlled Phase – Weeks 0 to 16: The summary on the numbers and percentages of the following subjects will be provided.
 - Subjects who completed the phase and entered the Apremilast Extension Phase (Weeks 16 to 52)
 - Subjects who completed the phase and did not enter the Apremilast Extension Phase (Weeks 16 to 52) as well as the reason
 - Subjects who discontinued early from the phase as well as the reason
- Apremilast Extension Phase – Weeks 16 to 52: The number and percentage of subjects who entered the phase, had at least one dose of Apremilast in the phase, completed the phase, and discontinued early will be provided. The primary reason for discontinuation from the treatment in this phase will also be summarized.
- Observational Follow-up Phase (4 weeks): Summary will be provided on the number and percentage of subjects who entered the phase, if not, the primary reason for not entering the phase, subjects who completed the phase, and if discontinued, the primary reason for not fulfilling follow-up visit 4 weeks after the completion or discontinuation of the study treatment.

The number and percentage of subjects randomized by study site and treatment arm will be tabulated. The percentages will be calculated based on the number of randomized subjects.

Listings will be provided for randomized subjects in analysis populations, for the reason of treatment or phase discontinuation, and for subjects excluded from the PP population along with the reason.

7. PROTOCOL DEVIATIONS

The protocol deviations and important protocol deviations were identified and assessed by clinical research physician or designee following company standard operational procedure. The protocol deviations and important protocol deviations will be summarized by treatment arm for the ITT population for the Placebo-controlled Phase and for the Apremilast Extension Phase.

A by-subject listing of subjects with protocol deviations and important protocol deviations in the ITT population will be provided. The important protocol deviations that lead to the exclusion of the subjects from the PP population will be flagged.

8. DEMOGRAPHICS AND BASELINE CHARACTERISTICS

The demographics, baseline characteristics, medical history, and Prior Psoriasis Medications will be summarized for the ITT population by treatment and overall. Individual subject listings will be provided to support the summary tables.

8.1. Demographics

Summary statistics will be provided for the following continuous variables:

- Age (years)
- Weight (kg)
- Height (cm)
- Baseline Body Mass Index (BMI; kg/m²), BMI will be calculated as: BMI (kg/m²) = Weight (kg)/ Height (m²)
- Waist circumference (cm)

Number and percentage will be provided for the following categorical variables:

- Age category (< 65, \geq 65 years)
- Sex (Male, Female)
- Race
- Country
- Alcohol intake (Current use, Former use, or Never use)
- Tobacco use (Never Smoked, Past Smoker, Current Smoker)
- Baseline BMI category (<18.5, 18.5 to < 25, 25 to < 30, \geq 30 kg/m²)

8.2. Baseline Disease Characteristics

Baseline clinical characteristics will be summarized descriptively by treatment arm, which will include the following:

- Duration of plaque psoriasis (from date of diagnosis to the date of informed consent; year, presented one digit after the decimal point)
- Duration of plaque psoriasis categories (< 10, 10 to < 20, \geq 20 years)
- The primary manifestations for stratifications: scalp psoriasis, nail psoriasis, palmoplantar psoriasis, genital psoriasis, and psoriasis in visible locations
- Baseline DLQI total score
- Baseline DLQI score categories (>10 to 20, >20)

Apremilast**Statistical Analysis Plan. Protocol CC-10004-PSOR-020****Amgen INC.**

- Baseline sPGA score of visible locations: 0 (clear), 1 (almost clear), 2 (mild), 3 (Moderate), 4 (Severe)
- Baseline ScPGA score: 0 (clear), 1 (almost clear), 2 (mild), 3 (Moderate), 4 (Severe)
- Number of affected nails: 0, 1, ≥ 2
- Baseline NAPSI score for the target nail
- Baseline sPGA-G score: 0 (clear), 1 (almost clear), 2 (mild), 3 (Moderate), 4 (Severe)
- Baseline PPPGA score: 0 (clear), 1 (almost clear), 2 (mild), 3 (Moderate), 4 (Severe)
- Baseline pruritus NRS score
- Baseline skin discomfort/Pain VAS score
- Baseline PASI score
- Baseline PASI score categories (3 to 5, >5 to 10)
- Baseline BSA (%)
- Baseline BSA (%) category (≤ 3 , >3 to 5, >5 to 10, >10)
- Baseline EQ-5D vas and EQ-5D index value
- Baseline WPAI: PSO: percentage of work missed due to Psoriasis and overall work impairment for those who were currently employed; percentage of work impairment and percentage of daily activity impairment due to Psoriasis among all subjects
- Baseline PNQ: the importance of each of the 25 treatment goals will be summarized with count (%) by missing, does not apply to me, not at all, somewhat, moderately, quite and very.

